Immunodeficiencies of interest	Comorbidity	Defined as ≥1 ICD-10 diagnosis code for immunodeficiency. Complete list in ANNEX 5. LIST OF DIAGNOSIS CODES FOR SELECT IMMUNODEFICIENCIES OF INTEREST.
Prior use of corticosteroids	Medication history	Defined as ≥1 prescription dispensing of a corticosteroid (as identified by ATC code[s]) in the 12 months prior to the index tofacitinib dispensing. Complete list in ANNEX 4. LIST OF ATC CODES FOR COMEDICATIONS OF INTEREST
Prior use of statins	Medication history	Defined as ≥1 prescription dispensing of a statin (as identified by ATC code[s]) in the 12 months prior to the index tofacitinib dispensing. Complete list in ANNEX 4. LIST OF ATC CODES FOR COMEDICATIONS OF INTEREST.

Table 3. Operational definitions of study variables in Système National des Données de Santé

Variable	Role	Operational definition
Prior use of any biologic	Medication history	Defined as ≥1 prescription dispensing of a biologic (as identified by ATC code[s]) in the 12 months prior to the index tofacitinib dispensing. Complete list in ANNEX 7. LIST OF ATC CODES FOR MEDICATIONS OF INTEREST TO AVOID WHILE TAKING TOFACITINIB.
Prior use of conventional synthetic DMARDs (csDMARDs)/ Immunomodulators	Medication history	Defined as ≥1 prescription dispensing of a csDMARD/ Immunomodulators (as identified by ATC code[s]) in the 12 months prior to the index tofacitinib dispensing. Complete list in ANNEX 7. LIST OF ATC CODES FOR MEDICATIONS OF INTEREST TO AVOID WHILE TAKING TOFACITINIB.
Prior use of MTX	Medication history	Defined as ≥1 prescription dispensing of MTX (as identified by ATC code L04AX03) in the 12 months prior to the index tofacitinib dispensing.
Prior use of anti-TB therapy	Medication history	Defined as ≥1 prescription dispensing of anti-TB therapy (as identified by ATC code[s]) in the 12 months prior to the index tofacitinib dispensing.
Prior vaccination	Medication history	Defined as ≥1 procedure code, ≥1 ICD-10 code and/or ≥1 reimbursed prescription (as identified by ATC code[s]) for a vaccination, overall and stratified by live and non-live vaccinations (if available) in the 12 months prior to the index tofacitinib dispensing. Complete list in ANNEX 4. LIST OF ATC CODES FOR COMEDICATIONS OF INTEREST.

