Initiating tofacitinib with ≥1 VTE risk factor(s)	Outcome: changes in use in patients with VTE risk factors	Defined as ≥1 VTE risk factor(s) (as listed and defined above) identified in the 12 months prior to the index tofacitinib dispensing.
Initiating tofacitinib with ≥1 VTE risk factors other than CV or malignancy risk factors	Outcome: changes in use in patients with VTE risk factors	The same definition as above but only limited to VTE risk factors other than CV or malignancy risk factors.
VTE risk factor scores	Outcome: changes in use in patients with VTE risk factors	Calculated as the sum of the number of VTE risk factors (as listed and defined above) identified in the 12 months prior to the index tofacitinib dispensing. Weighting of VTE risk factors may be considered as a sensitivity analysis to reflect the potential different
Number of UC patients with: ≥1 VTE risk factor; no prior alternative therapy (i.e., biologic); and an ADD >10 mg in Weeks 17-24, Weeks 25-32, Weeks 33-40 or Weeks 41-48 of follow-up	Outcome: changes in use in patients with VTE risk factors	importance of each risk factor. Defined as an UC patient meeting all of the following criteria: ≥1 VTE risk factor(s) (as listed and defined above) 12 months prior to the index tofacitinib prescription dispensing; 0 prescription medication dispensing for a biologic (as identified by ATC codes) in the 12 months prior to the index tofacitinib prescription dispensing; and an ADD of >10 mg in any of the intervals: Weeks 17-24, Weeks 25-32, Weeks 33-40 and Weeks 41-48 of follow-up (ADD defined in Section 9.3.3). Complete list of biologics in ANNEX 7. LIST OF ATC CODES FOR MEDICATIONS OF INTEREST TO AVOID WHILE TAKING TOFACITINIB.
Assessment of VTE risk; Section 9.3.2)	factors while receiving	tofacitinib therapy (duration of tofacitinib therapy defined in
VTE	Outcome: changes in use in patients with VTE risk factors	Defined as ≥1 ICD-10 diagnosis code for VTE while receiving tofacitinib therapy. List of VTE codes in ANNEX 12. LIST OF DIAGNOSIS CODES FOR VTE

Table 3. Operational definitions of study variables in Système National des Données de Santé

Variable	Role	Operational definition
Surgery, major	Outcome: changes in use in patients with VTE risk factors	Defined as ≥1 procedure code for a major surgery while receiving tofacitinib therapy.
MI	Outcome: changes in use in patients with VTE risk factors	Defined as ≥1 ICD-10 diagnosis code for an MI while receiving tofacitinib therapy.

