History of	Outcome: changes	Defined as ≥1 ICD-10 diagnosis code for hypertension or ≥1
hypertension	in use in patients	prescription dispensing (as identified by ATC code[s]) for an
	with CV risk	antihypertensive in the 12 months prior to the index
	factors	tofacitinib dispensing. Complete list in ANNEX 8. LIST OF
		ATC CODES FOR ANTIHYPERTENSIVES.

¹ Potential for very low sensitivity leading to misclassification. This variable will be reported if feasible

Table 3. Operational definitions of study variables in Système National des Données de Santé

Variable	Role	Operational definition
History of chronic kidney disease	Outcome: changes in use in patients with CV risk factors	Defined as ≥1 ICD-10 diagnosis code for chronic kidney disease in the 12 months prior to the index tofacitinib dispensing.
CV risk factor scores	Outcome: changes in use in patients with CV risk factors	Calculated as the sum of the number of CV risk factors (as listed and defined above) identified in the 12 months prior to the index tofacitinib dispensing. Weighting of CV risk factors may be considered as a sensitivity analysis to reflect the potential different importance of each risk factor.
Initiating tofacitinib with ≥1 CV risk factor (s)	Outcome: changes in use in patients with CV risk factors	Defined as ≥1 CV risk factor(s) (as listed and defined above) identified in the 12 months prior to the index tofacitinib dispensing (unless otherwise specified).
Initiating tofacitinib with ≥1 CV risk factor and no prior use of an alternative therapy (i.e., biologic)	Outcome: changes in use in patients with CV risk factors	Defined as ≥1 CV risk factor (as listed and defined above) identified in the 12 months prior to the day of the index tofacitinib dispensing and 0 prescription medication dispensing for an alternative therapy (i.e., biologic) in the 12 months prior to the date of the index tofacitinib prescription dispensing. Complete list of biologics in ANNEX 7. LIST OF ATC CODES FOR MEDICATIONS OF INTEREST TO AVOID WHILE TAKING TOFACITINIB.
Assessment of CV risk for versus < 65 years))	actors while receiving	tofacitinib therapy (will be stratified by sex and age (≥65 years

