Initiating tofacitinib with ≥1 malignancy risk factor	Outcome: changes in use in patients with malignancy risk factors	Defined as ≥1 malignancy risk factor(s) (as listed and defined above) identified in the 12 months prior to the index tofacitinib dispensing.
Initiating tofacitinib with ≥1 malignancy risk factor and no prior use of an alternative therapy (i.e., biologic)	Outcome: changes in use in patients with malignancy risk factors	Defined as ≥1 malignancy risk factor (as listed and defined above) identified in the 12 months prior to the index tofacitinib dispensing and 0 prescription medication dispensing for a biologic (as identified by ATC code) in the 12 months prior to the index tofacitinib prescription dispensing. Complete list of biologics in ANNEX 7. LIST OF ATC CODES FOR MEDICATIONS OF INTEREST TO AVOID WHILE TAKING TOFACITINIB.
Assessment of malignan versus < 65 years))	cy risk factors while re	ceiving tofacitinib therapy (will be stratified by age (>65 years
Age ≥65 years	Outcome: changes in use in patients with malignancy risk factors	Defined as age ≥65 years while receiving to facitinib.
Malignancy (non- metastatic and metastatic, excluding NMSC)	Outcome: changes in use in patients with malignancy risk factor	Defined as ≥1 ICD-10 diagnosis code for malignancy (excluding NMSC) while receiving tofacitinib therapy.
Current smoker	Outcome: changes in use in patients with malignancy risk factor	Defined as ≥1 ICD-10 diagnosis code for tobacco use disorder or ≥1 procedure code for counselling visits for smoking or ≥1 prescription dispensing (as identified by ATC code[s]) for a nicotine replacement product while receiving tofacitinib.

Table 3. Operational definitions of study variables in Système National des Données de Santé

Variable	Role	Operational definition
Discontinuation of	Outcome: changes	Defined as ≥1 malignancy risk factor while receiving
tofacitinib after	in use in patients	tofacitinib therapy (as listed and defined above) plus
developing ≥1	with malignancy	0 prescription dispensing for tofacitinib within a specific
malignancy risk	risk factor	time window after the code for the first malignancy risk
factors while taking		factor.
tofacitinib		
		Note: The time window for when to look for a tofacitinib prescription dispensing will be specific to the malignancy risk factor acquired while receiving tofacitinib therapy and will be operationalised during SAP development.

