		ANNEX 3. LIST OF DIAGNOSIS CODES FOR SELECT
		INFECTIONS OF INTEREST
Adherence to recommo	endations for limitation	ons of use with concomitant medications not compatible
with tofacitinib		
Variables will be presen	ted overall and may be	e stratified by patients with and without ≥2 tofacitinib
prescription reimbursem	ents during the follow	-up period (where the second prescription is reimbursed within
	f the days' supply [or t	the equivalent] of the first prescription), pending sufficient
sample size.		
Use of biologics	Outcome:	Defined as ≥30 overlapping days' supply of a tofacitinib
approved to treat RA,	Concomitant	prescription dispensing and a prescription dispensing for a
PsA or UC while	medications not	biologic approved to treat RA, PsA or UC (as identified by
taking tofacitinib	compatible with	ATC code[s]) during the follow-up period.
	tofacitinib	Complete list of biologics in ANNEX 7. LIST OF ATC
		CODES FOR MEDICATIONS OF INTEREST TO AVOID
		WHILE TAKING TOFACITINIB.
Use of selected potent	Outcome:	Defined as ≥30 overlapping days' supply of a tofacitinib
immunosuppressants	Concomitant	prescription reimbursement and a prescription reimbursed
while taking	medications not	for the selected potent immunosuppressants azathioprine, 6-
tofacitinib	compatible with	mercaptopurine, cyclosporine or tacrolimus (as identified by
	tofacitinib	ATC code[s]) during the follow-up period.
		Complete list of selected potent immunosuppressants in

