		ANNEX 7. LIST OF ATC CODES FOR MEDICATIONS
		OF INTEREST TO AVOID WHILE TAKING
		TOFACITINIB.
Receipt of a live	Outcome:	Defined as ≥1 CCAM procedure code or ≥1 ICD 10 code
vaccination while	Concomitant	and/or ≥1 prescription reimbursement (as identified by ATC
taking tofacitinib	medications not	code[s]) for a live vaccination (as available) while receiving
-	compatible with	tofacitinib therapy in the follow-up period.
	tofacitinib	Complete list of vaccinations in ANNEX 4. LIST OF ATC
		CODES FOR COMEDICATIONS OF INTERESTANNEX

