9.9. Limitations of the research methods

9.9.1. Internal validity of study design

9.9.1.1. Measurement error(s)/misclassifications(s)

The French SNDS and linked datasets are extracted from claims and hospital practice databases, plus death registries. The possibility of misclassification and miscoded data exists. However, the SNDS and its linked datasets have been extensively used to assess utilization and post-authorisation safety of new interventions, including for drugs used to treat UC, RA or PsA. ¹³⁻¹⁹

Tofacitinib exposure

Reimbursement data are used as a proxy for drug intake. Thus, the presence of a reimbursement for a drug does not indicate whether the medication was actually consumed or taken as prescribed. Given that tofacitinib is an expensive drug specifically prescribed by specialists, the likelihood of patients not taking the drug when dispensed is considered low. Furthermore, data from real-world studies have also demonstrated that adherence to tofacitinib treatment is typically very good among patients with UC, RA and PsA. ²⁰⁻²²

Prescriptions reimbursed in outpatient settings are fully captured by the SNDS and linked datasets. Though not all medications administered during hospital stays are fully captured by the SNDS, it is estimated that tofacitinib is predominantly reimbursed in outpatient settings. As such, the likelihood of misclassification of index tofacitinib treatment due to missing inpatient medication data is considered negligible.

Indication for tofacitinib initiation

Reason for drug prescription is not documented in either inpatient or outpatient settings. Therefore, a proxy will be used to determine indication, adapted from published algorithms which use hospital discharge diagnoses codes and diagnostic reason for registration in the LTD database.²³ The development of these algorithms will be informed by literature review and input from subject-level experts in RA, UC or PsA and separately from SNDS database experts.

Inaccurate (or missing) indication(s) being assigned to the index tofacitinib dispensing is possible with the proposed algorithm. However, registrations into the LTD database have

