9.9.2. Missing data and/or incomplete data

The French SNDS database and linked datasets are claims and hospital practice datasets where missing data are possible. Missing and/or incomplete data mainly applies to causes of death, which is not a variable of interest in this study. The use of multiple linked data sources (primary care, hospital, pharmacy data and central death registrations) has the potential to reduce missing and/or complete data and improve exposure and/or outcome ascertainment. Data on treatments administered over-the-counter or in hospital are not available (excluding for medications invoiced in addition to the hospital disease-related group) nor laboratory results, as described above.

To avoid missing or the input of inaccurate data, quality control processes are performed prior to the data being integrated in the SNDS.³¹

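### Where Table 3 names a record type for biologics it counts only prescription dispensings, so a patient whose only recent biologic was given in hospital would be scored as having had no alternative therapy

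*Protocol*

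**What the plan says.** Protocol section 9.3.1, Table 3, defines prior biologic use in the medication history as follows: "Defined as ≥1 prescription dispensing of a biologic (as identified by ATC code[s]) in the 12 months prior to the index tofacitinib dispensing". The same record type carries over to the outcomes:

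- UC with at least one VTE risk factor and a maintenance-phase dose above the threshold: "0 prescription medication dispensing for a biologic (as identified by ATC codes) in the 12 months prior to the index tofacitinib prescription dispensing".
- CV risk factor without prior alternative therapy: zero "dispensing for an alternative therapy (i.e., biologic) in the 12 months prior to the date of the index tofacitinib prescription dispensing".
- Malignancy risk factor without prior alternative therapy: "0 prescription medication dispensing for a biologic (as identified by ATC code) in the 12 months prior to the index tofacitinib prescription dispensing".
- Age 65 and over: the initiation row and the two continuation rows for patients who turn 65 also rest on dispensings.
- Concomitant biologic use: at least 30 overlapping days' supply of a tofacitinib "prescription dispensing and a prescription dispensing for a" listed biologic.

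Annex 7 supplies ATC codes only. By contrast, the Table 3 row for live vaccination accepts several record types. It begins "Defined as ≥1 CCAM procedure code or ≥1 ICD 10 code" and then adds reimbursed prescriptions.

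On the data source, section 9.9.2 states: "Data on treatments administered over-the-counter or in hospital are not available (excluding for medications invoiced in addition to the hospital disease-related group". Section 9.9.1.1 says that "not all medications administered during hospital stays are fully captured by the SNDS", but it assesses the consequence only for index tofacitinib, where it calls the risk negligible. Section 9.4 lists the hospital discharge database (PMSI) as one of the three components of the SNDS.

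**The concern.** Section 9.9.1.1 explains that absence of a prior biologic stands in for non-adherence to the recommendation to use tofacitinib only when nothing else is suitable. The protocol thus has a proxy built on one record type, a source that holds some hospital drug records and lacks others, and no statement of how the two fit together for biologics.

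Annex 7 lists agents such as infliximab, vedolizumab and rituximab. The protocol gives no routes or places of administration. I take it as an assumption that some listed agents are infused in hospital. On that footing, a patient with such treatment and no dispensed biologic in the look-back counts as having had no alternative, so an adherent prescription is scored as non-adherent. For concomitant use the same gap hides incompatible treatment and makes adherence look better than it is.

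**Working it through.** The protocol states no figure for biologic use or for hospital capture, so there is nothing to reproduce. The check compares the definitions and then illustrates the error with assumed inputs.

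**Step 1: who is misclassified.** Only a patient who (a) had a biologic in hospital during the look-back, (b) had no biologic dispensing in it, and (c) has no hospital record that is both captured and counted. A patient with infusions and one dispensed biologic is classified correctly.

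**Step 2: size.** Let p be the true share of starters with a prior biologic, f the share of those whose only look-back biologic was given in hospital, and c the share of that hospital use that is captured and counted.

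- Scored share with no prior biologic = (1 − p) + p·f·(1 − c)
- Upward error = p·f·(1 − c)

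None of p, f or c is in the documents. With p = 0.7 (true share 30%):

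| f | c = 0 | c = 0.5 | c = 1 |
|---|---|---|---|
| 0.1 | 37% | 33.5% | 30% |
| 0.3 | 51% | 40.5% | 30% |
| 0.5 | 65% | 47.5% | 30% |

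The error is 3.5 to 35 percentage points for c between 0.5 and 0, and nil at c = 1. With c = 0 and f from 0.1 to 0.5, a true share of 50% (p = 0.5) is scored 55% to 75%, and a true share of 10% (p = 0.9) is scored 19% to 55%.

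**Step 3: period contrasts.** The scored share equals 1 − p·k with k = 1 − f·(1 − c). If f and c are the same in every reporting period, a true change is multiplied by k. With f = 0.3 and c = 0, k = 0.7. A true fall from 30% to 10% (p from 0.7 to 0.9) is then scored as 51% to 37%, that is 14 points instead of 20. The levels are off by 21 and 27 points, the contrast by 6. A false trend needs f or c to change between periods.

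**Step 4: which analyses use the proxy.**

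- The sample size and primary comparison in section 9.5, and the named regressions in 9.7.2.4.1, 9.7.2.4.3 and 9.7.2.4.4, concern risk-factor proportions and scores. They do not use biologic history.
- In the CV and malignancy analysis sections, prior alternative therapy is a stratifier, subject to sample size.
- The UC proportion with a VTE risk factor in 9.7.2.4.1 depends on the proxy and is only described.
- The age 65 and over outcomes in 9.7.2.4.2 include proxy-based proportions and are also compared by logistic regression.

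**Step 5: concomitant use.** The overlap outcome needs days' supply. In its row on contraindicated immunosuppressants, Table 3 approximates this from the reimbursed package size and the recommended posology. That does not describe a hospital administration, so counting hospital records would also need a rule for the days each one covers.

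**The case against.** The strongest reply is that the exclusion is only implied. A reader might infer that hospital infusions never count, but no section says so. Section 9.9.2 says separately billed hospital drugs are available, the PMSI is part of the source, and the term for a dispensing is never restricted to retail pharmacies. Table 3 also switches loosely between dispensings and reimbursements. This stands, so the point is that the definitions do not provide for these records.

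A second reply is that 9.3.1 allows algorithms and code lists to be refined in the SAP, and Annex 7 says its codes will be verified. That answers a missing code. It does not answer the record type, which Table 3 has already fixed and which is broader for vaccination. Section 9.7 itself sends major changes to primary endpoint definitions to a protocol amendment.

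Third, a reader might extend the point to every biologic outcome. That goes too far. Sections 9.7.2.3.2 and 9.7.2.4.2 and the JAKi row of Table 3 mention biologic use without restricting it to dispensings. Two UC posology rows are labelled as no prior biologic but defined by at least one biologic dispensing. As written, a missed infusion removes patients from those rows, so the error runs the other way. The conflict of label and definition is a separate matter that needs reconciling.

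Fourth, section 9.9.1.1 already warns that the proxy may overstate non-adherence. Its reason is that suitability is not recorded. Missed hospital treatment is a different cause and is not mentioned for biologics.

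**Conclusion.** The point holds for the Table 3 definitions that name dispensings as their source: prior use, UC with a VTE risk factor, age 65 and over, CV, malignancy, and concomitant use. As written, they misclassify patients treated with a biologic only in hospital. The proportions without a prior biologic are biased upwards and concomitant biologic use downwards.

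The size is unknown. The illustration runs from no error to 35 points at p = 0.7, and the zero-capture column should not be taken as an estimate. The error is nil if separately billed records are counted and cover all hospital use.

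A reader might also infer that UC is hit hardest, or that a shift between infused and self-injected agents from 2018 to 2024 would show up as changed adherence. The documents give neither the place of administration nor the product mix, so neither can be asserted. If capture and mix are stable, levels suffer more than period contrasts. The main risk-factor proportion and score comparisons are unaffected. The point is still worth settling before extraction, because the proxy feeds outcomes under primary objective 2 and the remedy is simple.

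**What to change.** In Table 3, define biologic use, both prior and concomitant, as an outpatient dispensing or a hospital administration that the PMSI records as billed separately from the group tariff. Then:

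- add the hospital drug codes to Annex 7;
- state how many days each hospital administration covers, so that it can enter the 30-day overlap outcome;
- list any Annex 7 biologic whose hospital use is not captured, and report the proportions without a prior biologic as upper bounds with respect to that residual gap;
- add the gap, for biologics specifically, to the limitations in section 9.9.1.1.

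The cost is an addition to the code list and one more PMSI table from a source that the study already uses.
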